3.6.6 Electrocardiogram

Electrocardiogram parameters will be assessed using standard 12-lead electrocardiography. The following ECG parameters as well as the change from baseline for each of those parameters will be reported and descriptively summarized by treatment group at each of the specified time points: Heart rate (beats/min), RR (msec), PR (msec), QRS (msec), and QT (msec) intervals and the QT corrected interval.

The normality/abnormality of the ECG evaluation will be summarized using frequency tables of the number of subjects with a normal/abnormal ECG evaluation at each scheduled visit. A listing of subjects will be produced which will display all ECG findings in subjects with abnormal ECGs.

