4.3.2.3 Electrocardiograms

At the visits specified in [Table 4.2.1-1](#), [Table 4.2.2-1](#), and [Table 4.2.2-2](#), ECGs will be obtained after 10 minutes supine rest. Only a single ECG will be required at the specified time points. Only the overall evaluation will be recorded in the eCRF.

The same recorder will be used for each subject at each time point, if possible. Date and time settings should be checked at the start of each study day and aligned with an official timekeeper for all machines used in the study.

Skin preparation should be thorough and electrode positions should be according to standard 12-lead ECG placement.

In this study lead V2 will be analysed and reported as primary. Lead V5 will be analysed, for all visits, as backup for the individual where analysis in lead V2 is not deemed possible for predose or significant parts of whole visits or whole visits.

The following variables will be reported: heart rate, RR, PR, QRS, and QT intervals from the primary lead of the digital 12-lead ECG. The investigator may add extra 12-lead ECG safety assessments if there are any abnormal findings or if the investigator considers it is required for any other safety reason.

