3 STATISTICAL METHODS

3.1 General Considerations

Data will be presented in data listings sorted by cohort and treatment, subject number and date collected, where appropriate. Tabular summaries will be presented by cohort and treatment group. Categorical data will be summarized by the number and percentage of subjects within each category. In general, continuous variables will be summarized by descriptive statistics including mean, standard deviation, median, minimum, and maximum.

The last observation carried forward (LOCF) will be used in efficacy and pharmacodynamics (PD) endpoints analyses unless otherwise specified. Baseline values will be defined as the last valid assessment prior to the first administration of study treatment unless otherwise specified.

All statistical tests will be 2-sided at an alpha = 0.1 significance level unless stated otherwise. There will be no adjustment for multiplicity.

Data analyses will be performed using SAS[®] version 9.3 or higher (SAS Institute Inc., Cary, NC).

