3.6 Safety Analyses

The analyses will be based on the As-treated population. All safety summaries will be presented by treatment group for each cohort, unless otherwise specified.

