3.6.4 Clinical Laboratory Evaluations

Hematology, serum chemistry, and urinalysis laboratory evaluations will be performed during the study. The hematology and serum chemistry (including calcitonin, lipase, and amylase) parameters as well as their changes from baseline will be summarized with descriptive statistics (number of subjects, mean, and standard deviation, median, minimum and maximum) by treatment group at each of the time points specified in Treatment and Follow-up Period Study Procedures in the protocol. The urinalysis results will be listed. The hematology and serum chemistry results will also be classified as low, normal, or high. The urinalysis results will be classified as normal or abnormal. The shift from baseline hematology, serum chemistry, and urinalysis results will be summarized by treatment group at each of specified time points.

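### SAP 3.6.6 tabulates normal/abnormal ECGs by visit with no shift from baseline, so treatment-emergent ECG abnormality is not summarised by arm

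*SAP*

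**What the plan says.** SAP 3.6.6 plans three ECG outputs.

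- Numerical parameters: "The following ECG parameters as well as the change from baseline for each of those parameters will be reported". These are heart rate, the RR, PR, QRS and QT intervals, and corrected QT.
- The normal/abnormal evaluation, given as "frequency tables of the number of subjects with a normal/abnormal ECG evaluation at each scheduled visit".
- Subject-level data: "A listing of subjects will be produced which will display all ECG findings in subjects with abnormal ECGs".

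The layout rule in SAP 3.6 applies to the tables: "All safety summaries will be presented by treatment group for each cohort, unless otherwise specified".

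For laboratory results, SAP 3.6.4 goes one step further: "The shift from baseline hematology, serum chemistry, and urinalysis results will be summarized by treatment group at each of specified time points". Urinalysis in that section is classified on two levels, normal and abnormal. SAP 3.7 also splits anti-drug antibody status into positive at baseline only, positive at both, and positive after baseline only.

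On baseline, SAP 3.1 states: "Baseline values will be defined as the last valid assessment prior to the first administration of study treatment". The protocol schedules an ECG at screening (Table 4.2.1-1) and a predose ECG on Day 1 in both cohorts (Tables 4.2.2-1 and 4.2.2-2). On data capture, Protocol 4.3.2.3 says: "Only the overall evaluation will be recorded in the eCRF".

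**The concern.** ECG is a named measure under the secondary safety objective (Protocol 2.2), and the overall evaluation is the ECG result that goes into the eCRF. A normal ECG is not an entry requirement. Exclusion criteria 11 and 12 cover recent cardiovascular events or procedures and severe heart failure, and criterion 1 leaves other conditions to the investigator. Some subjects may therefore start with an abnormal ECG.

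In that setting, a count of abnormal ECGs at each visit mixes three groups: subjects abnormal throughout, subjects newly abnormal, and (by their absence) subjects who have reverted to normal. The set of subjects counted can also change between visits through withdrawal, and through the replacement allowed by Protocol 4.1.7.

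The comparison with placebo that a safety reader wants is how many subjects went from normal to abnormal in each arm. Protocol 3.2.3.1 says 300 µg is being given for longer than before. Protocol 3.2.3.2 reports a heart rate rise of 6.6 beats per minute (90% CI 4.1 to 9.1) after 7 days in earlier work. Protocol 4.4 lists QT prolongation among the possible reasons for suspending the study. A table whose percentages stay level could be read as showing no ECG change when it does not establish that.

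**Working it through.** The plan states no figure on this point, so there is none to reproduce. The check has two parts.

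**1. What each planned output gives.**

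| Output | Referenced to baseline? | Number going from normal to abnormal, by arm? |
|---|---|---|
| ECG evaluation by visit (SAP 3.6.6) | No | No |
| ECG parameters (SAP 3.6.6) | Yes, change from baseline | No; a summary of interval changes does not count subjects |
| ECG listing (SAP 3.6.6) | Subject by subject, if the baseline record is shown | Only by hand count |
| Treatment-emergent AEs (SAP 3.6.1) | Yes | Only findings that need intervention or are judged medically significant (Protocol 5.1) |
| Urinalysis, normal/abnormal (SAP 3.6.4) | Yes, shift | Yes, for urinalysis |

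**2. What visit counts leave open.** Take n subjects with an ECG at both baseline and the visit, a abnormal at baseline and b abnormal at the visit. Let x be the number newly abnormal.

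- The b − x persisting cases cannot exceed a, so x ≥ b − a. Also x ≥ 0.
- New cases cannot exceed b, nor the n − a subjects who began normal.
- Hence max(0, b − a) ≤ x ≤ min(b, n − a).

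The arm sizes come from Protocol 4.1.1 (Cohort 1: 26 active, 13 placebo). The baseline rates are **assumed**, because the documents give none. I take about 10%, 20% and 30%, with the same number abnormal at the visit (b = a) and no missing ECGs.

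| Arm | a = b | Range of x | Baseline-normal (n − a) | Upper end |
|---|---|---|---|---|
| Active, n = 26 | 3 | 0 to 3 | 23 | 3/23 = 13.0% |
| Active, n = 26 | 5 | 0 to 5 | 21 | 5/21 = 23.8% |
| Active, n = 26 | 8 | 0 to 8 | 18 | 8/18 = 44.4% |
| Placebo, n = 13 | 1 | 0 to 1 | 12 | 1/12 = 8.3% |
| Placebo, n = 13 | 3 | 0 to 3 | 10 | 3/10 = 30.0% |
| Placebo, n = 13 | 4 | 0 to 4 | 9 | 4/9 = 44.4% |

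Within each row the visit table looks the same over the whole range. With a = b, the range closes to a single value only if a = 0 or a = n. The upper ends are extremes: every baseline-abnormal subject would have to become normal while an equal number of others became abnormal. They show that the counts do not determine the answer. They do not predict what this trial would find.

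**The case against.** A reader might infer that new and pre-existing ECG abnormalities cannot be told apart in this trial. The documents do not support that. The sentence after the planned frequency tables provides a listing of all ECG findings in subjects with abnormal ECGs. SAP 3.1 orders listings by cohort, treatment, subject and date where appropriate. With at most 63 planned subjects, new cases can be counted from it, provided the baseline record is displayed, and the Day 1 column of the visit table gives an approximate baseline-normal denominator. ECG findings that matter clinically also enter the treatment-emergent AE tables by arm. The separation can be made; it is not planned as a summary.

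Other points on that side:

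- Protocol 4.8.4.1 asks only for descriptive summaries at each time point by treatment, and visit counts satisfy it. This is correct: the SAP does not depart from the protocol.
- Vital signs have no shift table either (SAP 3.6.5). They are numerical, however, and are summarised as change from baseline. The closer comparisons are urinalysis and antibody status, both categorical and both set against baseline.
- Table templates sit in a statistical programming plan (SAP 1) that is not among the documents. A shift table there can be neither confirmed nor excluded. The SAP itself names shifts for laboratory data and frequency tables for ECG.
- A shift table at each visit still has denominators that vary. This is true, but each subject is compared with their own baseline, so new and resolved cases no longer cancel.

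What remains is that a hand count from a listing is not a planned by-arm summary, and the AE tables omit new abnormalities below the threshold for reporting.

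**Conclusion.** The point holds as a minor reporting gap. The planned ECG tables do not summarise treatment-emergent abnormality by arm, although the same SAP does this for another normal/abnormal result. No primary or secondary efficacy conclusion is affected, and no information is lost.

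The size cannot be fixed from the documents because the baseline abnormality rate is not given. The ranges above, such as 0 to 5 of 21 baseline-normal active subjects, rest on assumed rates, equal counts at both times and complete ECGs. They are illustrative only. The conclusion also rests on the SAP text alone, since the programming plan is not available.

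**What to change.** In SAP 3.6.6, present the ECG evaluation as a normal/abnormal shift from baseline, by cohort and treatment, at each scheduled visit, in the format already used in SAP 3.6.4. The margins of that table keep the visit counts now planned.

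Use the SAP 3.1 baseline, the last valid assessment before first dose, rather than fixing it as the Day 1 ECG. A subject with no Day 1 recording but a valid screening ECG then keeps a baseline.

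Add one row per arm: subjects with any post-baseline abnormal ECG, out of those normal at baseline. Keep the subject listing and make sure it shows the baseline record.

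The cost is a wording change in the SAP and one table shell. The overall evaluation is already recorded in the eCRF, and no visit, test or data item is added.

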3.7 Immunogenicity

All subjects in the safety analysis set with reported anti-drug antibody (ADA) results (ADA positive or ADA negative, titer, cross-reactivity to GLP1 (positive or negative), cross-reactivity to glucagon (positive or negative) will be shown in the data listing.

ADA status (positive vs. negative) will be summarized by treatment group according to the following categories:

ADA prevalence: subjects who are ADA positive at any visit (including baseline)

Subjects who are ADA positive at baseline only

Subjects who are ADA positive at baseline and positive post baseline

Subjects who are ADA positive post-baseline only (treatment-induced ADA)

Subjects who are persistently positive; persistently positive is defined as at least 2 post-baseline ADA positive measurements (with ≥ 16 weeks apart) or an ADA positive result at the last available assessment

Proportion of subjects who are transiently positive; transiently positive is defined as at least one post-baseline ADA positive measurement and not fulfilling the conditions for persistently positive.

Proportion of subjects who are treatment-boosted ADA; treatment-boosted ADA is defined as baseline ADA titer that was boosted to a 4-fold or higher level following drug administration

ADA incidence (treatment-emergent ADA), defined as the sum of treatment-induced ADA (post-baseline positive only) and treatment-boosted ADA

Similar summary will be performed for ADA cross-reactivity to GLP-1 and/or glucagon (as data allows and if applicable).

The association of ADA status with PK, PD endpoints, efficacy, and safety may be evaluated if data allows and if applicable.

3.8 Pharmacokinetics

The analysis of the PK data is described below. Actual time of sampling, rather than nominal (planned) sampling time, will be used to derive PK parameters. Nominal sampling time will be used for the summary of PK concentrations and will be utilized in the descriptive summaries in mean and median plots. Missing PK parameters will not be imputed.

For subjects in each active treatment group the following pharmacokinetic parameters will be determined from the plasma concentration-time data for MEDI0382 if data allow. The pharmacokinetic parameters will be calculated by standard non-compartmental analysis according to current working practices and using Phoenix WinNonlin 6.3 or equivalent. All calculations of non-compartmental parameters will be based on actual sampling times.

The following PK parameters of MEDI0382 will be determined if data allow for each subject from the plasma concentration–time data:

1. C_{max} : The first occurrence of the maximum observed plasma concentration determined directly from the raw concentration-time data
2. t_{max} : The first time at which C_{max} is observed will be determined directly from the raw concentration-time data.
3. C_{τ} : trough concentrations from the plasma concentration-time data at the end of the dosing interval (i.e. 24 hours).
4. t half: The apparent terminal elimination half-life ($t_{1/2}$) obtained as the ratio of $\ln 2/\lambda_z$, where λ_z is the terminal phase rate constant estimated by linear regression analysis of the log transformed concentration-time data
5. AUC_{τ} : Area under the plasma concentration time curve at the end of the dosage interval τ .
6. R_o : observed accumulation ratio will be calculated using both the AUC and C_{trough} methods, where data allows, as follows: $R_o = AUC_{\tau day i}/AUC_{\tau day 1}$ and $R_o = C_{\tau day i}/C_{\tau day 1}$.

All the derived parameters described above will be listed. For each of these parameters, except t_{max} , the following summary statistics will be calculated for each active treatment group: median, maximum, minimum, arithmetic mean, standard deviation, CV, geometric mean. For t_{max} median, maximum, minimum, arithmetic mean.

Individual Ctrough will be listed by cohort, treatment and day and will be summarized as maximum, minimum, arithmetic mean and geometric mean.

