2.2 Secondary Objectives and Associated Endpoints

Table 2.2-1 Secondary Objectives and Associated Endpoints

Type	Objective	Endpoint
Efficacy	To assess the effects of MEDI0382 titrated up to a dose level of 300 µg on additional measures of glucose control and body weight versus placebo after 49 days of treatment (Cohort 1 only)	
 Change in HbA1c from baseline (Day - 1) to the end of 49 days of treatment Change in fasting plasma glucose (Day -1) from baseline to the end of 49 days of treatment Change in body weight (kg) from baseline (Day 1) to the end of 49 days of treatment Proportion of subjects achieving > 5% body weight loss from baseline (Day 1) after 49 days of treatment
Safety	To characterise the safety profile and tolerability of MEDI0382 titrated up to a dose level of 300 µg during dosing and follow-up (Cohorts 1 and 2)	Measures of safety and tolerability (24-hour heart rate and blood pressure, other vital signs, ECG, laboratory test results, and AEs)
PK, Immunogenicity	To characterise the PK profile and immunogenicity of 50 and 300µg of MEDI0382 (Cohorts 1 and 2)	
 PK endpoints for 50 µg MEDI0382 after 1, 7, and 14 days of treatment and 300 µg MEDI0382 after 1 and 28 days of treatment; AUC over a dosing duration, C_{max}, T_{max}, T_{1/2}, trough plasma concentration (C_{trough}), and accumulation ratio (C_{min} [R₀]) Development of anti-drug antibodies and titre (if confirmed positive)
Efficacy	To characterise the effect of 50 µg of MEDI0382 on glucose lowering versus placebo after 7 days (Cohorts 1 and 2)	Percentage change in glucose AUC as measured by a standardised MMTT from baseline (Day -1) to the end of 7 days of treatment

Table 2.2-1 Secondary Objectives and Associated Endpoints

Type	Objective	Endpoint
------	-----------	----------

AE = adverse event; AUC = area under the concentration-time curve; C_{max} = maximum observed concentration; C_{min} [R_0] = accumulation ratio; C_{trough} = trough plasma concentration;
ECG = electrocardiogram; HbA1c = glycated haemoglobin; MMTT = mixed-meal tolerance test;
PK = pharmacokinetic; $T_{1/2}$ = terminal half-life.

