3.2 Study Design and Dose Rationale

3.2.1 Dose Rationale

PK information collected in previous single and multiple dose clinical studies (Studies D5670C00001 and D5670C00002) suggest that MEDI0382 has a linear profile in the dose range 5 to 300 μ g with a half-life of approximately 8 to 13 hours, which allows minimal accumulation after repeat daily administration and achievement of steady state between 4 and 7 days. Moreover, the absorption profile in the low-dose range tested suggests that doses lower than 100 μ g may have a different bioavailability to doses greater than 100 μ g.

Based on PK/pharmacodynamics (PD) modelling conducted using available clinical data and from a literature review of GLP-1 and glucagon modulators, the maximal clinically efficacious dose for glucose control of MEDI0382 was predicted to be in the range of 200 to 300 μ g/day; in addition early clinical data from a prior single-ascending-dose study (Study D5670C00001) identified potentially efficacious doses in a range lower than 100 μ g. However, there is no information available on efficacy with repeat dosing at dose levels below 100 μ g. The initial dose for Cohorts 1 and 2 of this study is therefore proposed to be 50 μ g and the maximum dose to be administered in this study will not exceed 300 μ g/day. As

described above, the principle of dose up-titration to improve tolerability with higher doses is well established with short-acting GLP-1 analogues ([Victoza, 2014](#)).

The study is designed to provide efficacy information on glucose control and weight loss at 300 µg administered daily for 28 days to allow comparison with previous clinical data collected at 200 µg at a similar administration duration. It will also explore a prolonged dose titration schedule for repeated doses of MEDI0382 to characterise the safety/tolerability profile and PK/PD profile of MEDI0382 at a relevant pharmacological range to facilitate rational design of future studies. Moreover, it is designed to establish the efficacy of repeated dosing of 50 µg MEDI0382 on glucose control.

[REDACTED]

[REDACTED]

[REDACTED]

[REDACTED]

[REDACTED]

[REDACTED]	[REDACTED]	[REDACTED]	[REDACTED]	[REDACTED]
[REDACTED]	[REDACTED]	[REDACTED]	[REDACTED]	[REDACTED]
[REDACTED]	[REDACTED]	[REDACTED]	[REDACTED]	[REDACTED]
[REDACTED]	[REDACTED]	[REDACTED]	[REDACTED]	[REDACTED]
[REDACTED]	[REDACTED]	[REDACTED]	[REDACTED]	[REDACTED]
[REDACTED]	[REDACTED]	[REDACTED]	[REDACTED]	[REDACTED]

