- m Predose not applicable on Days 7, 29, 36, and 43. An additional blood test for safety (to be taken at any time between Day -3 and Day -7) is not required if the screening visit occurs within 7 days of dosing (Day 1); if the screening visit is more than 7 days prior to dosing on Day 1, then additional safety blood tests should be taken (as described in Section 4.3.3).
- n PK Sampling Schedule for MED10382:
Day -1; No specific time point
Day 1; Predose
Day 7 and Day 15; Predose
Day 22; Predose, 1, 2 (± 15 min); 4, 6, 8, and 12 (± 30 min) hours postdose
Day 23: Predose
Day 29; 36; 43 Predose
Day 49; Predose, 1, 2 (± 15 min); 4, 6, 8, and 12 (± 30 min) hours postdose
Day 50; Predose

^o ADA Sampling Schedule: Day 1 predose; Day 29 predose; Day 50 predose; and 28 days after administration of the last dose in the study

■ [REDACTED]

^q Capillary blood ketone (point-of-care testing) and serum beta-hydroxybutyrate will be measured at baseline after at least 10 hours fasting on Day -1 and predose and 4 hours postdose on Day 22, and Day 49 with fasting for at least 10 hours the night before.

^r MMTT Type A and B Schedule: Following a minimum 10-hour fast overnight and 2.5 hours after taking the IP, a blood sample for glucose (Type B) or glucose metabolism panel [REDACTED] will be taken immediately prior (within 15 minutes) to the subject drinking one entire can of Ensure Plus as a standardised meal (ie, “0 minutes”). Blood samples for glucose metabolism panel will additionally be drawn at 15, 30, 45, 60, 90, 120, 180, and 240 minutes (\pm 5 min) after consumption of the standardised meal.

^s MMTT Type C Schedule: the subject should be fasted from 1400 hours (\pm 15 min) and receive water only from this time until 2000 hours. A standardised liquid meal (one entire can of Ensure Plus) should be administered to the subject at 1800 hours. The subject should ensure that they are wearing their CGM device before, during, and after the test. No additional blood tests are required to be taken during this period, and the subject will be permitted to eat and drink freely from 2000 hours onwards.

^t CGM device should be worn continuously throughout the study and the sensor should be applied to the arm, taking into account subject preference and which side the ABPM device will be used on. The sensor applied to the skin is single-use and may not be re-attached once removed.

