4.8.5 Analysis of Immunogenicity/Pharmacokinetics

Pharmacokinetic parameters such as MEDI0382 C_{max} , T_{max} , AUC, and $T_{1/2}$ will be estimated if data allow, from plasma concentration time data for MEDI0382 at the 50 and 300 μg dose level separately.

Descriptive statistics will be generated for PK parameters for the MEDI0382 group in each cohort. Subjects who have at least one measurable concentration time point of investigational product will be used for this analysis.

The incidence and impact of ADA to MEDI0382 will be evaluated. The number and percentage of subjects with confirmed positive serum antibodies to MEDI0382 will be reported by dose level. Data on titres and cross-reactivity to GLP-1 and glucagon (where applicable) will be listed. If warranted by the data, the association of ADA positive with observed PK data may be explored.

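### The accumulation ratio planned at 300 µg has no first-dose denominator; the SAP formula is valid only for Cohort 2 at 50 µg

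*SAP*

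**What the plan says.** SAP 3.8 (Pharmacokinetics) states that the "observed accumulation ratio will be calculated using both the AUC and" trough "methods, where data allows, as follows": AUC over the dosing interval on day i divided by that on day 1, and the same for the trough. It does not name day i, require equal doses, or say what day 1 means after a dose step.

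Protocol 2.2 includes the accumulation ratio among the secondary PK endpoints, for 50 µg "MEDI0382 after 1, 7, and 14 days of treatment and 300" µg "after 1 and 28 days of treatment". Protocol 3.2.3.2 also places it in the PK profile at 50 and 300 µg, and gives troughs at other dose levels the separate job of showing steady state. Protocol 4.8.5 has parameters estimated at the 50 and 300 µg "dose level separately".

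Dosing (Protocol 3.1.2) and PK sampling (footnotes to Tables 4.2.2-1 and 4.2.2-2) are as follows.

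- **Cohort 1:** 50, 100 and 200 µg for 7 days each, then 300 µg for 28 days. Day 1 has a predose sample only, and no Day 2 sample is listed. The next entry is "Day 7 and Day 15; Predose". Full profiles are on Day 22 (first 300 µg dose) and Day 49, with 24-hour samples on Days 23 and 50.
- **Cohort 2:** 50, 100 and 200 µg for 14 days each, then 300 µg for 7 days. Full profiles are on Days 1, 7 and 14, all at 50 µg, with predose samples on Days 2, 8 and 15. Later samples are predose only, on Days 29, 43, 49 and 50.

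**The concern.** An accumulation ratio compares exposure under repeated dosing with exposure after a first dose of the same size. At 300 µg neither cohort supplies that first dose.

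In Cohort 1 the first 300 µg day is Day 22, and by then the subject has had a week at 200 µg. Protocol 3.2.1 puts steady state at 4 to 7 days, so Day 22 contains near-steady-state 200 µg exposure. This inflates the denominator and pulls the ratio towards 1. In Cohort 2 the first 300 µg dose is on Day 43, with no profile that day and no Day 44 sample.

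The bias runs in the direction the sponsor already expects, since Protocol 3.2.1 anticipates little build-up with daily dosing. A figure near 1 would look like confirmation when it is mostly produced by the titration.

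The unrestricted formula would also permit Cohort 2 troughs at 100 to 300 µg to be divided by the 50 µg Day 1 trough, which mixes accumulation with the dose step.

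**Working it through.** The documents state no numerical accumulation ratio, so there is no plan figure to reproduce.

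**Inputs.** Half-life 8 to 13 h, linear kinetics and steady state in 4 to 7 days (Protocol 3.2.1); dosing interval 24 h; dosing and sampling calendars as above. The absorption rate is not given and is assumed: instantaneous, or first-order at 0.5 or 0.2 per hour.

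**1. General result at 300 µg.** Let R be the true accumulation ratio and φ = 1/R. For AUC, φ is the fraction of a single dose's total AUC that falls in the first 24 h. Scale steady-state exposure to 1 per µg.

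- Day 49 = 300.
- Day 22 = 300φ + 200(1 − φ) = 200 + 100φ.
- Day 49 / Day 22 = 300/(200 + 100φ) = 3/(2 + φ).

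The same algebra holds for troughs, with φ the first-dose trough over the steady-state trough. The share of the excess over 1 that is hidden is 2/(2 + φ). Because φ cannot exceed 1, this is at least two thirds whatever the absorption rate.

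**2. Instantaneous absorption.** With r = 2^(−24/half-life), φ = 1 − r.

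- 8 h: r = 0.125, true R = 1/0.875 = 1.143, observed 3/2.875 = 1.043, hidden 2/2.875 = 70%.
- 13 h: r = 0.278, true R = 1/0.722 = 1.385, observed 3/2.722 = 1.102, hidden 2/2.722 = 73%.

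**3. Superposition over the exact Cohort 1 calendar.** The trough ratio is the Day 50 sample over the Day 23 sample.

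| Half-life | Absorption | True R, AUC | Day 49/Day 22, AUC | True R, trough | Day 50/Day 23, trough | Earlier-dose share of Day 22 AUC |
|---|---|---|---|---|---|---|
| 8 h | instantaneous | 1.143 | 1.043 | 1.143 | 1.043 | 8.7% |
| 8 h | 0.5/h | 1.178 | 1.053 | 1.143 | 1.043 | 10.6% |
| 8 h | 0.2/h | 1.273 | 1.077 | 1.152 | 1.046 | 15.4% |
| 13 h | instantaneous | 1.385 | 1.102 | 1.385 | 1.102 | 20.4% |
| 13 h | 0.5/h | 1.452 | 1.116 | 1.385 | 1.102 | 23.2% |
| 13 h | 0.2/h | 1.603 | 1.143 | 1.397 | 1.105 | 28.7% |

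**4. Cohort 2 at 50 µg.** Day 7 and Day 14 AUC over Day 1, and Day 8 and Day 15 predose over Day 2 predose, return the true R in every case. Here the formula is right.

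**5. Literal cross-dose trough ratios in Cohort 2.** Over the Day 2 predose trough, the formula gives (dose/50) × R with trough R of 1.14 to 1.40: Day 29 (after 100 µg) 2.3 to 2.8; Day 43 (after 200 µg) 4.6 to 5.6; Days 49 and 50 (after 300 µg) 6.9 to 8.4. These assume equal bioavailability across doses. The protocol doubts this, since doses below 100 µg "may have a different bioavailability to doses greater than" 100 µg, so dividing by dose is not a safe repair either.

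**The case against.** Four defences have force.

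- **The formula is not wrong under titration as such.** A reader might infer that it fails throughout. It does not: the Cohort 2 profiles on Days 1, 7 and 14 match the protocol's 50 µg endpoint days and give a correct ratio.
- **The missing Cohort 1 Day 1 profile is not an analysis error.** The where-data-allow qualifier covers it, and SAP 3.8 does not impute missing PK parameters. Cohort 1 simply yields no 50 µg ratio. The qualifier does not help at 300 µg, because the Day 22 and Day 49 samples exist.
- **Nobody plans the cross-dose trough ratios.** A reader might infer them from the SAP formula. Protocol 3.2.3.2 assigns troughs at other dose levels to steady state, and Protocol 4.8.5 keeps 50 and 300 µg apart. What stands is that SAP 3.8 does not repeat the restriction.
- **No section names Day 22 as the denominator.** That is an inference. It is a strong one: the protocol lists accumulation at 300 µg after 1 and 28 days, and Day 22 is the only sampled first 300 µg day. The alternative is that the listed 300 µg ratio cannot be formed at all, which the plan does not say.

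It is also fair that the narrow ranges rest on an absorption assumption for a subcutaneous product, and that the ratio is purely descriptive.

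**Conclusion.** The point holds for the 300 µg ratio. Day 49 over Day 22 in Cohort 1 would be reported near 1.04 to 1.10 when true accumulation is 1.14 to 1.39 (instantaneous absorption), or up to 1.14 against 1.60 for AUC with slow absorption. The exact figures depend on the half-life range and the assumed absorption. The direction, and the loss of at least two thirds of the excess over 1, need only linear, time-invariant kinetics with 200 µg at steady state by Day 21. Cohort 2 offers no substitute at 300 µg.

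For cross-dose troughs, the finding is only that the SAP wording is looser than the protocol's intent. The consequence is limited to one descriptive secondary PK parameter. The change is still worth making, because it is cheap and the biased figure would seem to support a prior expectation.

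**What to change.** In SAP 3.8, name the numerator and denominator days by cohort and dose:

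- **Accumulation ratio:** Cohort 2 at 50 µg only. AUC over the dosing interval on Days 7 and 14 over Day 1; predose troughs on Days 8 and 15 over Day 2.
- **Cross-dose trough ratios:** excluded explicitly. Later Cohort 2 troughs are listed and summarised by day and dose.
- **Cohort 1 at 300 µg:** report Day 22 and Day 49 AUC and the Day 23 and Day 50 troughs. If a ratio is shown, label it as relative to the first 300 µg day after 200 µg, not as accumulation.
- **Alternative for Cohort 1:** correct Day 22 for residual 200 µg exposure by superposition, using the Day 22 predose concentration and the terminal rate constant. In the 13 h example, Day 22 exposure of 272.2 less a residual of 55.6 leaves about 216.7, and 300/216.7 recovers 1.385. State the assumption that absorption of the earlier dose is essentially complete.

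The cost is SAP text and, for the correction, a short derivation. No samples or visits are added. The uncorrected 300 µg accumulation ratio is lost or relabelled. The protocol endpoint wording should be aligned at the next amendment, or the difference recorded in the SAP as a departure from the protocol.
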